- a) **Specific Aim 1: Collect preliminary data on the psychiatric outcomes of pregnant women with Bipolar Disorder who undergo a TDM protocol for lamotrigine.** Hypothesis: Women undergoing a TDM protocol for lamotrigine will have a low rate (defined as <30%) of psychiatric relapse. Psychiatric outcomes will be defined by clinician interview, the Edinburgh Postnatal Rating Scale (EPDS) and the Young Mania Rating Scale (YMRS).
- b) **Specific Aim 2: Collect adverse event data from pregnant women with Bipolar Disorder undergoing a TDM protocol for lamotrigine.** Adverse event data will be collected using the UKU side effect semi-structured interview and the Frequency, Intensity, and Burden of Side Effects Rating (FIBSER) scale.
- c) **Specific Aim 3: Collect preliminary data on the obstetrical outcomes of pregnant women with Bipolar Disorder who undergo a TDM protocol for lamotrigine.** Obstetrical outcomes will be defined by review of the delivery admission chart by an obstetrician using the Peripartum Events Scale (PES).
- d) **Specific Aim 4: Collect preliminary data on infant outcomes whose mothers underwent a TDM protocol for lamotrigine.** Pediatric outcomes will be defined by review of the infant delivery chart by a pediatrician and by a neurobehavioral assessment using the Neonatal Intensive Care Unit (NICU) Network Behavioral Scale (NNS).

3. Background:

Evidence indicates that serum levels of lamotrigine decrease by 200-250% across pregnancy¹⁹, and that the clearance of lamotrigine can be increased 10-fold across pregnancy in many but not all women²⁰. In the epilepsy literature, levels between 2.5 and 15 have been reported for therapeutic efficacy with higher levels correlated with increasing signs of toxicity²¹. In the epilepsy literature, there is a published protocol for lamotrigine management before, during, and after pregnancy²² for seizure control as follows:

- *Prior to pregnancy, adjust lamotrigine dose to minimum effective dose to attain clinical stability. Obtain a reference concentration (RC), preferably when the patient is not taking oral contraceptives.*
- *During pregnancy, monitor lamotrigine concentration every 4 weeks. If serum concentration falls below RC, increase lamotrigine dose by 20-25% and re-measure serum level after 4 additional weeks. If serum level does not fall below RC, maintain same dose but check level again in four weeks.*

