b) **Maternal Adverse Event Outcomes:** Adverse events will be monitored by using a semi-structured interview, (the UKU side effects rating scale) at every visit as well as the self-rated Frequency, Intensity and Burden of Side Effects Rating scale (FIBSER). Adverse events will be considered as related to the TDM protocol if they were not present at baseline or worsened in severity and were noted after a change in dosing. A preliminary analysis will be conducted comparing adverse events in participants who underwent dose increases during pregnancy to those that did not (assuming there are participants who did not undergo dosage increase).

c) **Maternal Obstetrical Outcomes:** Maternal obstetrical outcomes will be extracted from the delivery admission chart which will be reviewed by the study obstetrician, [name]. The Perinatal Events Scale (PES) will be used to collect a majority of these outcomes including Past Obstetrics History, Medical Risk Factors, Obstetric Risk Factors, Progress in Labor, Method of Delivery and Complications. A preliminary analysis will be conducted comparing obstetrical outcomes in participants who underwent dose increases in pregnancy to those that did not (assuming there are participants who did not undergo dosage increase).

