d) **Newborn Outcomes:** Newborn outcomes will be extracted from the delivery admission chart which will be reviewed by the study pediatrician, [name]. We will use the infant outcomes portion of the Peripartum Events Scale (which includes Apgar scores and Infant Complications) and, in addition, collect infant weight, measurements, gestational age and need for medical interventions or NICU admission. A preliminary analysis will be conducted comparing infant outcomes for participants who underwent dose increases during pregnancy to those that did not (assuming there are participants who did not undergo dosage increase). All infants will also undergo a neurobehavioral assessment at weeks 2, 4 and 6 postpartum using the Neonatal Intensive Care Unit (NICU) Network Behavioral Scale (NNS). Our research assistant will receive training at the Brown Center for the Study of Children at Risk which has a standardized training on the use of NNS. The NNS will be used to identify any infant neurobehavioral effects of the TDM protocol. A preliminary analysis will be conducted comparing infant neurobehavioral outcomes for participants who underwent dose increases during pregnancy to those that did not (assuming there are participants who did not undergo dosage increase).

- b. **Study duration and number of study visits required of research participants.** Each subject will be seen approximately 12 times across the course of the study. We will attempt to recruit subjects who are less than 20 weeks pregnant and will plan for monthly study visits during pregnancy. Women and their infants will also be assessed after delivery at 1, 2, 4, and 6 weeks postpartum. We expect that most study visits will take place in the Women's Mood Disorders Center, however home visits by research assistants will be used if a participant cannot come to the Center (for example if a participant is on bedrest) to maintain participation and continuity.
- c. **Blinding, including justification for blinding or not blinding the trial, if applicable.** Not applicable. Subjects will be receiving the drug that is part of their usual care and we will be collecting pilot data.
- d. **Justification of why participants will not receive routine care or will have current therapy stopped.** Participants will undergo more clinical care than is currently routine in that they will be monitored on a monthly basis and their lamotrigine dosing adjusted as part of a TDM protocol.

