- e. **Justification for inclusion of a placebo or non-treatment group.** There will be no placebo or non-treatment group.

- f. **Definition of treatment failure or participant removal criteria.** Participants will be removed from the study if they meet criteria for Relapse as described above. Participants will also be removed if they are lost to follow-up or are noncompliant with the study protocol.
- g. **Description of what happens to participants receiving therapy when study ends or if a participant's participation in the study ends prematurely.** Participants will return for clinical care to their outpatient provider at the end of the study or if their participation ends prematurely.

5. Inclusion/Exclusion Criteria

Inclusion Criteria. Pregnant women with a history of Bipolar Disorder (Bipolar Disorder I, Bipolar Disorder II or Bipolar Disorder not otherwise specified) who are taking lamotrigine and who intend to continue lamotrigine through pregnancy will be enrolled. All participants must be in the first 20 weeks of pregnancy at the time of enrollment. All participants must also be on stable doses of lamotrigine (for the past 4 weeks), have an EPDS <13, a YMRS <12 and be judged by the study clinician to be clinically stable. Participants may be taking other psychiatric and nonpsychiatric medications.

Exclusion Criteria. Participants who have active suicidal ideation or who are clinically unstable will be excluded. Participants who are dependent on alcohol, marijuana or other substances in the 90 days prior to study entry will be excluded.

6. Drugs/ Substances/ Devices

- a. **The rationale for choosing the drug and dose or for choosing the device to be used.** Lamotrigine is an evidence-based treatment for Bipolar Disorder in pregnancy. The rationale for our TDM/dosing regimen is based on recommendations in the epilepsy literature. There is currently no established protocol for the dosing of these drugs in pregnant patients with Bipolar Disorder.
- b. **Justification and safety information if FDA approved drugs will be administered for non-FDA approved indications or if doses or routes of administration or participant populations are changed.** There are no drugs with FDA approval for the management of mood disorders in pregnancy. Therefore, we must use FDA approved drugs for non-FDA approved indications, a common clinical practice.

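### Obstetrical outcomes come only from the delivery admission chart, so a pregnancy that ends without a delivery admission contributes none, although women enrol in the first 20 weeks

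*Protocol*

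**What the plan says.** The Abstract (Section 1) states that obstetrical and infant outcomes are collected, with adverse events, to judge whether the monitoring protocol is safe. Four parts of the protocol then bear on who contributes an obstetrical outcome.

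- **Section 2, Aim 3:** "Obstetrical outcomes will be defined by review of the delivery admission chart by an obstetrician using the Peripartum Events Scale (PES").
- **Section 4a, Data Collection c:** "Maternal obstetrical outcomes will be extracted from the delivery admission chart which will be reviewed by the study obstetrician". The scale is said to supply most of these outcomes, "including Past Obstetrics History, Medical Risk Factors, Obstetric Risk Factors, Progress in Labor, Method of Delivery and Complications". Obstetrical outcomes are then to be compared between women who had dose increases in pregnancy and those who did not.
- **Section 5:** "All participants must be in the first 20 weeks of pregnancy at the time of enrollment".
- **Section 8c:** serious adverse events go to the IRB.

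For infants, Aim 4 has two sources: "Pediatric outcomes will be defined by review of the infant delivery chart by a pediatrician and by a neurobehavioral assessment".

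**The concern.** The data source acts as a selection rule. A woman may enrol early, have her levels followed, possibly have her dose raised, and then lose the pregnancy without ever being admitted for delivery. Read as written, she has no chart to review and drops out of both the numerator and the denominator of Aim 3.

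The bias runs one way. The omitted cases are adverse pregnancy outcomes, so a summary restricted to women with a delivery chart can look safer than one covering all enrolled women, and never less safe on this item. Section 4a hopes the data will support a multisite randomized trial and describes the study as the largest of its kind. With at most 20 women, one or two missing cases are a visible share of the safety information.

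There is a smaller defect in the same paragraph. Past obstetric history is listed among the outcomes, and obstetrical outcomes are then compared by dose increase. History that predates enrolment cannot result from dosing.

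**Working it through.** **1. Could another section supply the missing outcome?**

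| Place in the protocol | What it collects | Does it make a loss a study outcome? |
|---|---|---|
| Aim 2; Data Collection b | UKU and FIBSER side-effect ratings | No, loss is not named |
| Aim 3; Data Collection c | Chart review. The scale covers most items, but all come from the delivery admission chart | Only if there is a delivery admission |
| Aim 4; Data Collection d | Delivery chart review and infant neurobehavioral examination | No, needs a born infant |
| Section 4a, later visits | 1, 2, 4 and 6 weeks, counted from delivery | No |
| Section 7 | Outcomes will be described | No |
| Section 8c | Serious adverse events to the IRB | No, a reporting duty not linked to Aim 3 |

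Miscarriage, termination, fetal loss and stillbirth are not named as outcomes anywhere. The protocol fixes this definition and its source itself, so it is not a detail left to an analysis plan.

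**2. The denominator.** Section 4a recruits up to 20 women to keep 16, allowing 4 drop-outs: 4/20 = 20%, and 16/(1 − 0.20) = 20. The figure reproduces. The point does not depend on it beyond using n = 20.

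**3. How likely is an affected case?** The documents give no loss rate, so p, the proportion of pregnancies lost after enrolment without a delivery admission, is an assumption shown over a range. Expected losses = 20p. Chance of at least one = 1 − (1 − p)^20.

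| Assumed p | Expected losses in 20 | Chance of at least one |
|---|---|---|
| 1% | 0.2 | 18% |
| 2% | 0.4 | 33% |
| 5% | 1.0 | 64% |
| 10% | 2.0 | 88% |
| 15% | 3.0 | 96% |

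**4. What would the report show?** Suppose, as an invented illustration, that 2 of 20 pregnancies were lost without a delivery admission.

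- All enrolled women: 2/20 = 10% lost (exact 95% CI 1.2% to 31.7%).
- Women with a delivery chart: 0/18 (exact 95% CI 0 to 18.5%).

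If 3 of the 18 deliveries were also adverse, the two summaries would be 5/20 = 25% and 3/18 = 17%.

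**5. The dose-increase comparison.** Levels are drawn monthly and an increase follows a low level. A pregnancy that ends early has fewer levels and so less opportunity for an increase. Leaving losses out selects the comparison on reaching delivery. Adding them under a simple ever/never split would place most of them in the no-increase group merely because follow-up was short. This is immortal-time bias and would make dose increases look protective.

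**The case against.** **Aim 4.** A reader might infer that the infant outcomes are equally defective. The documents do not support that. Aim 4 concerns born infants and also uses a neurobehavioral examination, so conditioning on birth belongs to the aim. It needs only to be stated.

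**Late losses.** A reader might infer that every loss, including stillbirth, disappears. A stillbirth or late loss managed in a delivery admission would have a chart. The gap is losses without such an admission, mainly early ones.

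**Other records.** Monthly clinical evaluation would probably bring a loss to light, and a serious event would reach the IRB. So a loss need not vanish from the study's records. It would still lie outside the defined outcomes.

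**Risk factors.** It is tempting to call the medical and obstetric risk factors baseline items as well. The text does not say they predate enrolment, and the scale is not reproduced. Some may arise during the pregnancy, and removing those would discard real safety outcomes. Only past obstetric history clearly predates the study.

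**Size.** The loss rates are assumed, and enrolment as late as 20 weeks makes the low end possible. The intervals for 3/18 (about 4% to 41%) and 5/20 (about 9% to 49%) overlap heavily, and the aims are descriptive, with no decision rule. This is fair. The point concerns which women are counted, not a failed test.

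**Feasibility.** The provider release in Section 8b is framed around emergencies and may not clearly cover routine outcome collection. Section 4f removes women who relapse, are lost to follow-up or do not comply, so a full denominator needs some contact after removal. Both points stand and affect the cost of the fix.

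**Conclusion.** The concern holds for Aim 3 and Data Collection c. As defined, the obstetrical outcomes leave out any pregnancy that ends without a delivery admission, although these data are meant to assess safety and women enrol in the first 20 weeks. Reporting to the IRB does not repair this.

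The size cannot be taken from the documents. Over an assumed 1% to 15%, between 0.2 and 3 of 20 women would be affected, with an 18% to 96% chance of at least one. The calculation assumes that 20 women enrol, that losses are independent, and that the assumed rate counts only losses without a delivery admission. The direction of bias, towards a more favourable safety summary, does not depend on the rate.

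The primary relapse endpoint and the stated sample size do not change. The listing of past obstetric history among outcomes is a lesser fault in the same paragraph.

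**What to change.** In Aim 3 and Data Collection c:

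1. Record pregnancy outcome for every enrolled woman as live birth, stillbirth, miscarriage, termination or unknown, ascertained from the participant or her obstetrician.
2. Report it descriptively with all enrolled women as the denominator. Show women who were removed or lost to follow-up as unknown where the outcome was not obtained.
3. Keep the delivery items of the scale for women who deliver, and state that Aim 4 infant outcomes are conditional on birth.
4. Keep pregnancy loss out of the simple increase versus no-increase comparison. Describe each loss with its timing and any earlier dose changes.
5. Report past obstetric history as a baseline characteristic. Keep medical or obstetric risk factors that arise after enrolment as outcomes.

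The cost is protocol wording, one case-report item and a little extra follow-up contact, including with women removed early. Obstetricians' contact details and signed releases are already held under Section 8b, but the sponsor should confirm that the release covers routine outcome collection. No visit or laboratory test is added. The reported safety proportion may look less favourable.

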Our primary hypothesis is that prophylactic TDM for lamotrigine will result in a lower than expected rate of psychiatric relapse. The study will be an unblinded pilot study testing a TDM protocol for lamotrigine and will examine psychiatric, adverse event, obstetrical and infant outcomes. Because this is a pilot study we have chosen not to recruit a comparison group of women and instead focus on collecting outcomes for a larger sample of women who will undergo TDM for lamotrigine. Based on the literature we would expect the relapse rate in women who are maintained on their pre-pregnancy lamotrigine dosage to be at least 30%^{1,2}. Although our study design will not demonstrate superiority, it will provide preliminary evidence of efficacy and safety data for both the participant and her infant and will be the largest study examining a specific approach to managing lamotrigine during pregnancy in patients with Bipolar Disorder. We hope these data will then serve as a basis for a multisite randomized trial of prophylactic TDM for lamotrigine compared to treatment as usual in the future.

Pregnant women with Bipolar Disorder who are taking lamotrigine will be evaluated monthly during pregnancy including a clinical evaluation and a blood draw for lamotrigine levels at each visit. Based on the TDM protocol described below their lamotrigine dosing will be adjusted as needed based on their blood levels compared to the RC that was obtained prior to pregnancy or early in pregnancy while clinically stable. After delivery women and their infants will be assessed at 1, 2, 4, and 6 weeks postpartum.

Sample Size. We will recruit and follow up to 20 women with Bipolar Disorder who have chosen to take lamotrigine during pregnancy with a goal of maintaining a sample size of 16 allowing 4 drop-outs.

Recruitment. Participants will primarily be recruited through the Johns Hopkins Women's Mood Disorders Center (WMDC) and through referrals from the Obstetrics department. We will advertise on the WMDC Facebook site, the WMDC research site, EPIC and in local publications.

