Lamotrigine Dosing Adjustments. At the time of study enrollment each participant will have a RC defined based on either 1) a pre-pregnancy serum level (for the current lamotrigine dosage) or 2) a serum level drawn at the time of enrollment. While we will preferentially use a pre-pregnancy RC since pregnancy hormone levels can affect lamotrigine levels, many psychiatrists do not routinely check lamotrigine levels and from a practical perspective we will obtain a lamotrigine at study entry to promote study participation and recruitment. Participants will be clinically well at the time of enrollment so that the serum level will be correlated with clinical stability. Lamotrigine levels will then be drawn monthly and the dose adjusted to maintain the RC. Specifically, if the monthly serum level is more than 0.5µg/mL lower than the RC, the dose will be adjusted by 20-25% and checked again at the next monthly visit. Higher levels than the RC are unlikely, since levels generally decrease across the course of pregnancy, but the dose will not be adjusted down unless there is a clinical indication (i.e. toxicity). Postpartum, all participants will be instructed to taper to the lamotrigine dose that was being taken at the time of the RC over the course of two weeks. While this does not follow the exact neurology, protocol described above (Background), we believe this approach makes sense since it will be more consistent and avoid the potential problem of toxicity. It also follows the recommendations of Clark et al²³.

Data Collection

a) **Maternal Psychiatric Outcomes:** We will monitor maternal psychiatric outcomes based on the EPDS, YMRS and clinical interview. The primary endpoint is the proportion of women who experience psychiatric relapse from the time of enrollment to 6 weeks postpartum. **Relapse** will be defined as one of the following: meeting SCID criteria for a Major Depressive Episode, meeting SCID criteria for a hypomanic or manic episode, development of high risk suicidal plan or attempt, or psychiatric hospitalization.

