- If the participant is not at risk of harming herself or others but is psychiatrically ill, the study psychiatrist will provide clinical care as necessary until the participant can be seen by her treating outpatient clinical psychiatrist. The participant will remain in the study and undergo all study visits and procedures as long as consent continues.

Obstetrical Urgency/Emergency: Should one of the participants develop an urgent obstetrical problem, the participant will either be taken to the local Obstetrics and Gynecology Clinic or Emergency Room, whichever seems more appropriate. Both the Clinic and the Emergency Room are on the same campus as the study site. The subject's private obstetrician will also be contacted.

Lamotrigine toxicity: Every participant will be monitored closely for side effects/signs of toxicity during the trial. Because the RC will be established prior to pregnancy or early in pregnancy we anticipate that the likelihood of significant side effects or toxicity in the participants is very low. If a participant does develop side effects or signs of toxicity the dose of lamotrigine will be lowered by the study psychiatrist. At every visit the participant will fill out a Frequency, Intensity and Burden of Side Effect Scale (FIBSER) to monitor for significant side effects from the protocol. Obstetrical outcomes will be assessed by [name] from the Gynecology and Obstetrics Department.

Neonatal toxicity: It is possible that increased dosing of lamotrigine during pregnancy will lead to increased side effects or toxicity in the newborn. We do not anticipate this outcome since the protocol is used in the management of seizure disorders and there have not been reports of adverse effects in infants whose mothers participate in these protocols. We will monitor for this potential risk by collecting neonatal outcomes via a review of the medical record by a pediatrician ([name]) and by undergoing a neurobehavioral exam using the Neonatal Intensive Care Unit (NICU) Network Behavioral Scale (NNNS) at 2, 4, and 6 weeks postpartum. Our research assistant will undergo specialized training at Brown University in order to conduct the exam appropriately.

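### The dose trigger reads a single monthly level without fixing the draw time or checking for recently missed doses, so a mistimed draw or a recent miss can raise the dose

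*Protocol*

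**What the plan says.** The dosing rule is in Protocol section 4.a, Lamotrigine Dosing Adjustments. The RC is one serum level, either from before pregnancy or drawn at enrollment. After that, "Lamotrigine levels will then be drawn monthly and the dose adjusted to maintain the RC". When a monthly level is more than 0.5 µg/mL below the RC, "the dose will be adjusted by 20-25% and checked again at the next monthly visit". The section expects levels above the RC to be unlikely and adds that "the dose will not be adjusted down unless there is a clinical indication (i.e. toxicity"). Section 8.b (Lamotrigine toxicity) words the exception a little more widely: "If a participant does develop side effects or signs of toxicity the dose of lamotrigine will be lowered by the study psychiatrist".

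The visits that feed the rule are described in section 4.a as monthly, "including a clinical evaluation and a blood draw for lamotrigine levels at each visit". Section 4.f removes women who do not comply with the protocol, but gives no measure of missed doses. No section sets a draw time relative to the last dose, asks for that time, or asks about missed doses before the trigger is read.

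Dose increases are also used in the analysis. Section 4.a (Data Collection) plans preliminary analyses "comparing adverse events in participants who underwent dose increases during pregnancy to those that did not" and "comparing infant outcomes for participants who underwent dose increases during pregnancy to those that did not". It counts an adverse event as related to the monitoring protocol when it is new or worse and appears after a dosing change.

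**The concern.** A serum level can be low because clearance has risen, because the sample was drawn later after the dose than the RC sample, or because a recent dose was missed. The monitoring protocol is designed to correct only the first. As written, the rule takes the same step for all three, and the next check is a month away.

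If a missed dose or a late draw was the whole cause, and the woman then takes the higher dose in full, her level sits above her RC until clearance catches up. The rule does not bring it down unless she has side effects or signs of toxicity.

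Interpretation is affected too. The group with dose increases would mix faster clearance with missed doses and late draws, and an adverse event after such an increase would be attributed to the monitoring protocol. Monthly levels alone do not show which cause applied. This is a dosing procedure and the intervention under study, so it belongs in the protocol and not in a statistical analysis plan.

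**Working it through.** The protocol gives no figure on this point to reproduce: it offers no derivation of the 0.5 µg/mL margin.

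**Inputs from the protocol.** The trigger is a level below RC - 0.5 µg/mL, and the step is 20-25% (section 4.a). For a range of RC values I use section 3, where "levels between 2.5 and 15 have been reported for therapeutic efficacy with higher levels correlated with increasing signs of toxicity". Its units are not stated; I take them as µg/mL.

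**Assumptions, because the protocol is silent.** Once-daily dosing; half-life T of 12, 24 or 36 h; single-exponential decline; steady state; for the missed-dose case, samples drawn just before the next dose.

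**1. Last dose missed.** Level / RC = 0.5^(24/T), which is 0.25, 0.50 and 0.63.

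| RC | T = 12 h | T = 24 h | T = 36 h | Trigger below |
|---|---|---|---|---|
| 2.5 | 0.62 | 1.25 | 1.57 | 2.0 |
| 5 | 1.25 | 2.50 | 3.15 | 4.5 |
| 15 | 3.75 | 7.50 | 9.45 | 14.5 |

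The trigger trips in every cell.

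**2. One earlier dose missed.** With r = 0.5^(24/T), missing only the k-th last dose leaves 1 - (1 - r) x r^(k-1) of the RC.

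- Second-last: 0.81, 0.75, 0.77. At RC 5 (4.06, 3.75, 3.83) it trips for all three half-lives. At RC 2.5 (2.03, 1.88, 1.92) it trips for 24 and 36 h.
- Third-last: 0.95, 0.88, 0.85. At RC 5 (4.77, 4.38, 4.27) it trips for 24 and 36 h. At RC 2.5 (2.38, 2.19, 2.13) it does not trip.
- Fourth-last: 0.99, 0.94, 0.91. It does not trip at RC 5 (4.94, 4.69, 4.54) or at RC 2.5.

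So at RC 2.5-5 an isolated miss matters only within about the last three doses. The window is longer at a higher RC. The longest case here is RC 15 with T = 36 h: the sixth-last dose leaves 0.963 x 15 = 14.45 (trips) and the seventh-last leaves 0.977 x 15 = 14.65 (does not). A recall window of about a week covers all of these cases.

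**3. No dose missed, but a draw 6 h later after the dose than the RC draw.** Level / RC = 0.5^(6/T), which is 0.707, 0.841 and 0.891.

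- RC 5: 3.54, 4.20, 4.45 against 4.5. It trips for all three half-lives.
- RC 2.5: 1.77, 2.10, 2.23 against 2.0. It trips only for 12 h.

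**4. Size of the resulting excess.** One step with full intake and unchanged clearance gives 1.20-1.25 x RC, which is 6.0-6.25 at RC 5. This stays within the reported range for RC up to 15/1.25 = 12. If clearance rises 10%, the excess falls to 1.20/1.10 = 1.09 to 1.25/1.10 = 1.14 x RC. If it rises 20-25%, the excess is gone (1.20/1.20 = 1.25/1.25 = 1.00).

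**The case against.** The strongest defense is that the rule follows its source. The published epilepsy algorithm, as reproduced in section 3, also takes a 20-25% step on a single low level and states no timing or adherence check. This protocol is more cautious, since it asks for a fall of more than 0.5 µg/mL. The monthly clinical evaluation could cover missed doses, and section 4.f deals with noncompliance. Levels are expected to fall in pregnancy, so many triggers will be genuine. Any excess is limited by rising clearance, by UKU and FIBSER ratings at every visit, by dose lowering for side effects or toxicity, and by the postpartum taper.

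Most of this stands, and it keeps the point small. It does not close the gap. Nothing requires the clinical evaluation to ask about missed doses or record the answer. Removal for noncompliance is undefined and would not catch one missed dose or a late draw.

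A reader might infer that false triggers are common, or that women will be pushed to toxic levels. The documents support neither. A rate would need a within-person variation that the protocol does not give, and a level that stays flat, which sections 3 and 4.a do not expect. One unneeded step stays inside the reported range up to RC 12. Nor is the primary endpoint compromised directly: relapse is defined clinically and is not computed from levels. The comparisons by dose increase are labeled preliminary and depend on some women having no increase.

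**Conclusion.** The point holds as a gap in how the dosing rule is fixed. Followed as written, the rule raises the dose by 20-25% for a late draw or a recently missed dose just as it does for faster clearance, and does not reverse the step in pregnancy without a clinical indication. The trigger is easily reached on last-dose misses and, at RC 5, on a 6 h shift in draw time. It is not reached by isolated misses more than about three doses back at RC 2.5-5. The resulting excess is at most 1.20-1.25 x RC per step and shrinks as clearance rises.

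These sizes rest on assumed once-daily dosing, a half-life of 12-36 h and the simple decline model. The direction does not depend on the exact values. The frequency cannot be derived from the protocol. I rate this as a worthwhile, inexpensive improvement.

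**What to change.** In section 4.a, Lamotrigine Dosing Adjustments:

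- Draw monthly levels, and the RC when it is taken at enrollment, at a consistent time before the next dose where feasible.
- At each draw, record the time of the last dose and any doses missed in roughly the week before. A whole-month recall would be poorly aimed: a miss weeks earlier barely moves the level, but would mislabel a genuine clearance-driven increase.
- Have the study psychiatrist review both answers before an increase, with the option to repeat the level when a recent dose was missed or the timing was clearly off. Recording alone would leave the trigger unchanged.
- Report, as counts, the dose increases that followed a recent missed dose or a mistimed draw.

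**Cost.** Two data fields at visits already held. With about 12 visits per woman, 4 of them postpartum, there are about 12 - 4 = 8 pregnancy visits, so at most about 8 x 20 = 160 records. An occasional repeat draw may be needed, and a needed increase could be slightly delayed. Self-report is imperfect, and a pre-pregnancy RC, which the protocol prefers, may have no known draw time. With 16-20 women the counts are descriptive only.
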